9. STATISTICAL CONSIDERATIONS

9.1. General Design Issues

In the proposed single-arm phase II trial, we define favorable impact on the neurocognitive outcome as at least 0.5 standard deviation (SD) improvement in performance on attention measures (measured as described above) after administration of C7. That is, impact on the outcome is determined by whether a treatment causes at least 0.5 SD improvement on the primary attention measure for that age group in a single arm trial and the interest is **primarily focused on reaching a decision on whether to progress with C7 to a future larger trial**. (Note: The SD is a normative parameter provided with the testing instruments). The evidence to make this decision is evaluated by testing the null hypothesis that the true efficacy rate is less than or equal to some pre-specified value. It is desirable to achieve this goal whilst minimizing the number of subjects exposed to a novel agent. Here, we use the Simon's optimal two-stage design that yields the smallest expected sample size when the null hypothesis is true.

We apply Simon's optimal two-stage design (24) using as primary outcome attention performance for each of three age groups. At least 0.5 SD improvement in performance on the primary attention measure after the administration of C7 is considered a favorable outcome. The measurement of 0.5 SD improvement is commonly accepted as the cutoff for a minimally clinically important difference, as described in various studies (e.g., 32, 33).

This protocol will yield data that allow a clear **go/ no-go decision** regarding whether C7 should proceed to an efficacy trial:

- If a favorable outcome occurs in less than 50% of subjects, we will recommend that C7 not proceed to an efficacy trial.
- If a favorable outcome occurs in at least 80% of subjects, we will recommend that C7 proceed to an efficacy trial.

The sample size estimation for this optimal two-stage design is given in Section 9.3.

If an intermediate number of subjects (51 – 79%) exhibit a favorable primary attention outcome, the rest of outcomes, including the long-term, 6-month responses, will be considered for the go/ no-go decision on the basis of impact on these outcomes and the disease process, in addition to tolerability and safety indicators.

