Clinical significance and meaningfulness of the primary neurocognitive (attention) outcome: Attention is a core cognitive function that permits access to other areas of cognition and is commonly impaired in association with seizure disorders. Existing research has indicated that dietary interventions have the potential to promote attention functioning in children with G1D (26, 27). With regard to long-term outcomes, research in the field of childhood absence epilepsy has shown that even after attaining seizure freedom, attention deficits may remain (28). In other words, even normal EEG findings may not correspond to functional neuropsychological improvements. These findings in the field of childhood absence epilepsy are significant for the present study given that EEG seizures are more common than observable seizures in children with G1D. Additionally, these findings with regard to childhood absence epilepsy may help explain why language functioning improvements in children with G1D after administration of triheptanoin were not statistically significant in a previous trial (1). Again, attention is a core cognitive function that permits access to other areas of cognition (including language) and is commonly impaired in association with seizure disorders. For all of these reasons, attention functioning as measured by neuropsychological testing (described below in 6.3.9) may be a more relevant primary outcome for the present study than EEG findings. As noted above, the measurement of 0.5 SD improvement is commonly accepted as the cutoff for a minimally clinically important difference, as described in various studies (e.g., 32, 33), and thus in the present study we will look for this degree of improvement in performance on the primary measure of attention to answer the go/no-go decision for each age group.

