9.3. Sample Size and Accrual

We estimated the sample size using the primary outcome (attention) for each of three age groups. The same method will be applied for sample size estimation in each of three age groups. An improvement of 0.5 SD or more on the primary attention measure

after the administration of C7 is considered a favorable outcome. This study will yield data that allow a clear go/no-go decision regarding whether C7 should proceed to an efficacy trial: If a favorable outcome occurs in less than 50% of subjects, we will recommend that C7 not proceed to an efficacy trial. If a favorable outcome occurs in at least 80% of subjects, we will recommend that C7 proceed to an efficacy trial.

The sample size was estimated using Simon's optimal two-stage design (24). The null hypothesis that the proportion of favorable outcome is 50% will be tested against a one-sided alternative hypothesis that the proportion of favorable outcome is 80%. In the first stage, 7 subjects will be accrued. If there are 4 or fewer favorable outcomes in these 7 subjects, the study will be stopped, and we will recommend that C7 not proceed to an efficacy trial. Otherwise, 6 additional subjects will be accrued for a total of 13 subjects. If 8 or fewer favorable outcomes are observed in 13 subjects by the end of stage two, then no further investigation of C7 is warranted. This design yields a type I error rate of 0.1 and power of 80% when the true favorable outcome occurs in 80% of subjects. We plan to recruit 15 subjects with an expected 15% dropout rate resulting in 13 subjects for each age group. That is, we will recruit a total of 45 subjects for this protocol.

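### Sections 9.1 and 9.3 give different decisions at 7/13 and 8/13 in an age group; the stated alpha of 0.1 and power of 80% hold only if the Simon limit binds

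*Combined protocol and SAP*

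**What the plan says.** Section 9.3 tests a favorable-outcome rate of 50% against 80%, one-sided, separately in each of three age groups. After 7 subjects: "If there are 4 or fewer favorable outcomes in these 7 subjects, the study will be stopped". Otherwise 6 more are accrued, and at the end: "If 8 or fewer favorable outcomes are observed in 13 subjects by the end of stage two, then no further investigation of C7 is warranted". The section then claims: "This design yields a type I error rate of 0.1 and power of 80% when the true favorable outcome occurs in 80% of subjects". On numbers: "We plan to recruit 15 subjects with an expected 15% dropout rate resulting in 13 subjects for each age group".

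Section 9.1 gives a rule in observed percentages. Below 50% is a no-go, and 80% or more is a go. Between these comes the clause that begins "If an intermediate number of subjects (51 – 79%) exhibit a favorable primary attention outcome, the rest of outcomes", which brings the other outcomes, together with tolerability and safety, into the go/no-go decision. The same section ties the decision to a hypothesis test ("The evidence to make this decision is evaluated by testing the null hypothesis that the true efficacy rate is less than or equal to" a pre-specified value) and says the 0.5 SD criterion is used "to answer the go/no-go decision for each age group".

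**The concern.** At 7/13 and 8/13 the Simon limit says no-go, while the percentage band says the matter is still open. The band also sits badly with Section 9.1's own statement that the decision rests on testing the null hypothesis, because at these counts that hypothesis is not rejected.

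The go/no-go recommendation is what the trial is for, and it is open-label. If nothing ranks the two rules, the choice between them can be made after all the outcomes have been seen. The false-go rate is then no longer the 0.1 that the plan states; it depends on a judgement that the plan does not define.

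**Working it through.** **Inputs (Section 9.3 unless noted).** Null rate 0.50; alternative 0.80; one-sided; stage 1 n = 7, stop at 4 or fewer; total n = 13, no-go at 8 or fewer. Band 51–79%, automatic go at 80% or more (Section 9.1).

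**Which counts conflict.** 6/13 = 46.2%, no-go under both rules. 7/13 = 53.8% and 8/13 = 61.5%, no-go under 9.3 but open under 9.1. 9/13 = 69.2% and 10/13 = 76.9% clear the Simon limit and are open under 9.1, which is compatible. 11/13 = 84.6%, go under both. So 7 and 8 are the only final counts in conflict.

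**Formula.** For final total t, after continuing past stage 1,

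P(T = t) = Σ over x = 5, 6, 7 of C(7,x) p^x (1−p)^(7−x) × C(6,t−x) p^(t−x) (1−p)^(6−t+x).

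At p = 0.5 every term has denominator 2^13 = 8192, and the stage 1 weights for x = 5, 6, 7 are 21, 7 and 1:

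- t = 7: 21×15 + 7×6 + 1×1 = 358, so 0.0437
- t = 8: 21×20 + 7×15 + 1×6 = 531, so 0.0648
- t = 9: 21×15 + 7×20 + 1×15 = 470; t = 10: 21×6 + 7×15 + 1×20 = 251; together 721, so 0.0880
- t = 11, 12, 13: 78 + 13 + 1 = 92, so 0.0112

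| Result | True 50% | True 80% |
|---|---|---|
| Stopped at stage 1 | 0.7734 | 0.1480 |
| 5–6/13 | 0.0188 | 0.0005 |
| 7/13 | 0.0437 | 0.0048 |
| 8/13 | 0.0648 | 0.0285 |
| 9–10/13 | 0.0880 | 0.3165 |
| 11/13 or more | 0.0112 | 0.5017 |

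Both columns sum to 1.

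**The plan's own figures.** P(9/13 or more) = 0.0880 + 0.0112 = 0.0992 at 50%, and 0.3165 + 0.5017 = 0.8182 at 80%. These agree with the stated 0.1 and 80%. An exhaustive search for the optimal design with these rates (alpha at most 0.1, power at least 0.8) returns the same 4/7 and 8/13. The design is correctly derived.

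**If the band governs, stage 1 stop kept.** Let g be the share of 7–10/13 results that become a go when the true rate is 50%. P(7–10/13) = (358 + 531 + 721)/8192 = 1610/8192 = 0.1965, so

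alpha = 0.0112 + 0.1965 g.

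- g = 0: 0.011
- g = 0.5: (92 + 805)/8192 = 0.109
- g = 1: 1702/8192 = 0.208
- alpha equals 0.0992 at g = (0.0992 − 0.0112)/0.1965 = 0.45

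If every result at 9/13 or more is a go and 8/13 may go as well, the upper end is 0.0992 + 0.0648 = 0.164.

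Power at a true 80% = 0.5017 + (0.0048 + 0.0285 + 0.3165) h = 0.5017 + 0.3498 h, where h is the corresponding share at that rate. It runs from 0.50 (h = 0) to 0.85 (h = 1).

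**How often the conflict arises.** P(7–8/13) per group is 0.109 at a true 50%, 0.132 at 60%, 0.096 at 70% and 0.033 at 80%.

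**The case against.** **The specific text should win.** Section 9.3 is explicit, and Section 9.1 refers to it for the two-stage design, so a careful reader would treat 8/13 as a no-go and confine discretion to 9–10/13. This is a sensible reading, and it is the one recommended below. It makes the defect one of wording. But neither section says so, and Section 9.1 states the band without any such limit.

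**Stage 1 should then be in conflict too**, since 4/7 is 57%. A reader might infer this, but the documents support it only weakly. The band reads as a rule for completed results, while 9.3 gives a direct instruction to stop at 4/7. That result is not counted here.

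**Alpha doubles to 0.208.** This is the tempting strong reading, and the documents do not support it. The band lets the other outcomes, tolerability and safety lead to a no-go as well as a go, and it makes 9–10/13 discretionary too. The figure of 0.208 needs every 7–10/13 result to go. If fewer than about 45% go, alpha is below the design value. What stands is that alpha is undetermined.

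**The band may be meant for the pooled subjects.** Its sentence names no age group, and Section 9.5 estimates one proportion before comparing groups. This cannot be excluded. But Section 9.1 applies the Simon design by age group and refers to the decision for each age group, and Section 9.3 repeats the 50% and 80% limits next to the per-group design.

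**A ranking may exist elsewhere.** Part of the text between Sections 9.3 and 9.5 was not available for this review, so its absence from the plan cannot be asserted. This lowers confidence.

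**Conclusion.** The point stands as a conflict between two decision rules at 7/13 and 8/13 in an age group, with medium confidence. The Simon design and its stated alpha and power are correct if its limit binds. If the band governs, alpha per group is fixed only to the range 0.011 to 0.208, and power at a true 80% to 0.50 to 0.85. The conflict itself arises with probability 0.109 per group at the null and 0.033 at the design alternative, so it is narrow, but it falls on the trial's main decision.

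This rests on 13 evaluable subjects per group, the stage 1 stop being followed, the band applying by age group, and no ranking in the text that was unavailable.

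A reader might also infer that the plan claims 80% power for its automatic go. It does not: the stated power goes with the Simon limit. The automatic go (11/13 or more) has probability 0.50 at a true 80%, and the plan gives no figure for it.

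**What to change.** In Sections 9.1 and 9.3, state one rule in counts per age group:

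- 4/7 or fewer, and 8/13 or fewer: no-go (the Simon limits bind).
- 9–10/13: decided on the other outcomes, tolerability and safety. This replaces the 51–79% band.
- 11/13 or more: automatic go.

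State that alpha 0.1 and power 80% refer to clearing the limit at 9/13 or more, and that the automatic go has a probability of about 0.50 at a true 80%. Under this rule alpha is at most 0.099 however the discretion at 9–10/13 is used.

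Fix the denominator as well. Fifteen subjects are recruited per group and Section 9.5 plans multiple imputation, so 14 or 15 may contribute. Either specify that the test uses the first 13 evaluable subjects in each group, or give the matching limits for 14 and 15.

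Cost: wording only, with no extra subjects. The sponsor gives up discretion at 7–8/13 (probability 0.033 per group at a true 80%) and has to report a less favourable figure for the automatic go. Letting the Simon limit prevail is not the only way to reconcile the sections, but it is the one that keeps the error rates already stated.

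Whether the stage 1 stop applies to the age group or to the whole trial is a separate wording question. It should be reconciled too, but it is not part of this point.

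### The stated 0.1 type I error and 80% power describe the Simon boundary (9 of 13), not the automatic 'proceed' rule (observed 80%, i.e. 11 of 13), and the two rules are not reconciled

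*Combined protocol and SAP*

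**What the plan says.** Section 9.3 of the combined protocol and SAP gives the hypotheses for each age group: "The null hypothesis that the proportion of favorable outcome is 50% will be tested against a one-sided alternative hypothesis that the proportion of favorable outcome" takes the value 80%. The Simon boundaries follow. On the size of stage 1: "In the first stage, 7 subjects will be accrued". On stopping at that point: "If there are 4 or fewer favorable outcomes in these 7 subjects, the study will be stopped". On going further: "Otherwise, 6 additional subjects will be accrued for a total of 13 subjects". On the final boundary: "If 8 or fewer favorable outcomes are observed in 13 subjects by the end of stage two, then no further investigation of C7 is warranted". The operating characteristics come directly after: "This design yields a type I error rate of 0.1 and power of 80% when the true favorable outcome occurs in 80% of subjects".

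A second rule for the same endpoint appears in 9.1 and is repeated in 9.3 just before the Simon boundaries. Fewer than 50% favorable outcomes means a recommendation against an efficacy trial; at the other end, "If a favorable outcome occurs in at least 80% of subjects, we will recommend that C7 proceed to an efficacy trial". Section 9.1 alone adds a middle zone: "If an intermediate number of subjects (51 – 79%) exhibit a favorable primary attention outcome, the rest of outcomes, including the long-term, 6-month responses, will be" weighed in the decision, together with tolerability and safety. No error rates are given for the 80% threshold or for the middle zone.

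**The concern.** The figure 80% does two jobs. In the Simon calculation it is the true response rate under the alternative. In the recommendation rule it is the rate that must be observed before the plan automatically says proceed. If the true rate is 80%, the observed rate falls below 80% about as often as it reaches it, so a rule that demands an observed 80% cannot have 80% power at that true rate with this sample size.

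Section 9.1 makes the decision on whether to move to a larger trial the main purpose of the study and promises that the decision will be clear. The only error rates offered in support belong to the Simon boundary. A result of 9 or 10 of 13 could be reported as positive (null rejected under 9.3) or as inconclusive (middle zone under 9.1), and the choice could be made after the data are seen.

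**Working it through.** **Inputs.** From 9.3: null rate 0.50, alternative 0.80, one-sided; 7 subjects in stage 1, continue with 5 or more; 6 more in stage 2; positive with 9 or more of 13. From 9.1 and 9.3: automatic proceed at an observed rate of 80% or more. From 9.1: middle zone 51–79%. All figures are per age group.

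**1. Reproduce the plan's figures.** With X1 ~ Bin(7, p) and X2 ~ Bin(6, p), P(pass) = Σ over x = 5, 6, 7 of P(X1 = x) × P(X2 ≥ 9 − x).

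- p = 0.80: 0.2753 × 0.9011 + 0.3670 × 0.9830 + 0.2097 × 0.9984 = 0.2480 + 0.3608 + 0.2094 = 0.8182.
- p = 0.50: (21 × 22 + 7 × 42 + 1 × 57) / 8192 = 813/8192 = 0.0992.

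Both agree with the stated 80% and 0.1. A search over two-stage designs with type I error at most 0.10 and power at least 0.80 also returns 4/7, 8/13 as the optimal one (expected size 8.36 under the null).

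**2. Turn the observed-80% rule into a count.** 0.80 × 13 = 10.4, so 11 are needed: 10/13 = 76.9% and 11/13 = 84.6%.

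**3. Probability of an automatic proceed.** Eleven or more of 13 leaves at most 2 failures, so stage 1 must have had at least 5 of 7. The stage 1 stop therefore changes nothing, and the plain binomial tail applies.

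- p = 0.80: 78 × 0.8^11 × 0.2^2 + 13 × 0.8^12 × 0.2 + 0.8^13 = 0.2680 + 0.1787 + 0.0550 = 0.5017.
- p = 0.50: (78 + 13 + 1)/8192 = 92/8192 = 0.0112.

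The same formula gives 0.692 at a true rate of 85% and 0.866 at 90%.

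**4. Results of 9 or 10 of 13 after passing stage 1.**

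- p = 0.80: 0.8182 − 0.5017 = 0.3165 (0.317 before rounding the terms).
- p = 0.50: (813 − 92)/8192 = 721/8192 = 0.0880.

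**5. Three zones, taking 8 or fewer of 13 (or a stage 1 stop) as no-go.**

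| True rate | Automatic go (≥11/13) | Intermediate (9–10/13) | No-go |
|---|---|---|---|
| 50% | 0.011 | 0.088 | 0.901 |
| 80% | 0.502 | 0.317 | 0.182 |

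The 80% row adds to 1.001 through rounding. A go from the intermediate zone has no stated criterion, so its probability can be anything from none to all of that column. The chance of any go lies between 0.502 and 0.818 at a true rate of 80%, and between 0.011 and 0.099 at 50%.

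**6. Number evaluable.** Section 9.3 recruits 15 and expects 13. If 14 are evaluable, 12 are needed (11/14 = 78.6%) and the single-stage probability at a true rate of 80% is 0.448. If 15 are evaluable, 12/15 is exactly 80% and the probability is 0.648. All are below 0.80.

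**7. Lower overlap.** Results of 7/13 (53.8%) and 8/13 (61.5%) end investigation under 9.3 but are intermediate under 9.1. After passing stage 1 they have probability (21 × 35 + 7 × 21 + 1 × 7)/8192 = 889/8192 = 0.109 at a true rate of 50%. If 9.1 governed there, the upper limit for a false go would be (813 + 889)/8192 = 0.208, against 0.099 in step 5.

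**The case against.** The sponsor can fairly say that the quoted sentence refers to the design just described and is right. A reader might infer from the 0.50 that the stated power was miscalculated; it was not, as step 1 shows.

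The sponsor can also say that the upper end holds no formal contradiction. Section 9.3 says when not to proceed and never says that 9 of 13 means proceed. Passing the Simon boundary can be read as necessary, an observed 80% as sufficient, and the range between as a deliberate judgement zone. That is a legitimate design, and power to reject the null is the usual figure to quote for it. This stands, and it rules out two stronger readings. One is that an observed 80% is the only route to a go: 9.1 leaves a discretionary go open at 9 and 10 of 13, so 0.50 is a floor for the chance of a go, not the power of the whole decision. The other is that the real type I error is 0.01: with the judgement zone kept, 0.011 is also only a floor.

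One defence fails. The 50% and 80% thresholds cannot be read as true rates, because 9.1 defines the middle zone by the share of subjects who show a favorable outcome, which is an observed result. And a necessary-and-sufficient reading, though workable, is not written down and does not settle 7 and 8 of 13.

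Finally, the 0.50 depends on the denominator. Recruiting 15 and imputing missing data (9.5) could make it 15. That changes the size (0.65) but not the conclusion.

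**Conclusion.** The point holds as an inconsistency between decision rules. The 0.1 and 80% are correct for the Simon boundary and do not describe the automatic proceed rule printed beside it. With 13 evaluable subjects per age group, a treatment with a true rate of exactly 80% gets the automatic go with probability 0.50, goes to an open judgement with probability 0.317, and gets a no-go with probability 0.182. The overall chance of a go cannot be stated more closely than 0.50 to 0.82 at a true rate of 80%, and 0.011 to 0.099 at 50%.

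These figures assume independent subjects with a common response rate, 13 evaluable per group, and 8 or fewer of 13 taken as no-go, as 9.3 says. Sample size, the stage 1 stop and the exact binomial estimation in 9.5 are not affected.

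**What to change.** Name one governing decision rule and word it identically in 9.1 and 9.3, before outcomes are known. Two forms would work.

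- **Use the Simon boundary.** Define proceed as at least 5 of 7 and then at least 9 of 13. The stated 0.1 and 80% then describe the decision as they stand. The sponsor gives up the judgement zone at 9–10 of 13.
- **Keep three zones.** State the probability of automatic go, intermediate and no-go at a true rate of 50% (0.011, 0.088, 0.901) and 80% (0.502, 0.317, 0.182). Say that 80% is the power to pass the Simon boundary and not the chance of an automatic go. Do not quote 0.01 alone as the type I error while the judgement zone remains. Writing down a criterion for the intermediate zone would narrow the ranges.

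Under either form, say in the same edit which section governs at 7 and 8 of 13, and give the thresholds as counts, with the rule to apply if 14 or 15 subjects are evaluable. The cost is wording and restated figures in 9.1 and 9.3, with no extra subjects.

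### Section 9.3 states 80% power for exactly 13 subjects per age group, but at the plan's own 15% dropout the average power of the 8/13 rule is about 75%

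*Combined protocol and SAP*

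**What the plan says.** Section 9.1 applies the design separately by age: "We apply Simon's optimal two-stage design (24) using as primary outcome attention performance for each of three age groups". Section 9.3 gives the hypotheses: "The null hypothesis that the proportion of favorable outcome is 50% will be tested against a one-sided alternative hypothesis", the alternative being 80%. The first stage is "In the first stage, 7 subjects will be accrued", with the rule "If there are 4 or fewer favorable outcomes in these 7 subjects, the study will be stopped". Six more subjects bring the total to 13. The final rule is negative "If 8 or fewer favorable outcomes are observed in 13 subjects by the end of stage two", so a group needs at least 9 of 13 to proceed. The section claims a type I error of 0.1 and power of 80%.

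Recruitment is then set by "We plan to recruit 15 subjects with an expected 15% dropout rate resulting in 13 subjects for each age group", which gives 45 over three groups.

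Sections 9.1, 9.3 and 9.5 give no cut-off for any final number other than 13. They do not say whether dropouts are replaced or counted as unfavourable, or whether a fourteenth or fifteenth evaluable subject enters the test. Section 9.5 says missing data will be multiply imputed, but does not connect this to the integer cut-offs.

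**The concern.** The plan treats 13 as the result of recruiting 15, when it is only near the expected value. A group that ends at 11 or 12 and must still show 9 favourable outcomes faces a harder test than the one whose power is quoted. A group that ends at 14 or 15 and needs only 9 faces an easier one.

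The stake is the go/no-go decision. Because the trial is open-label, a cut-off chosen once the attained number is known would be chosen with the results in view. For example, 9 of 14 is a go if the cut-off of 8 is kept. It is a no-go if the cut-off is reset to hold the error below 0.10 at 14 (at least 10 of 14).

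**Working it through.** **Inputs.** From section 9.3: null rate 0.50; alternative 0.80; one-sided; stop at 4 or fewer of 7; negative at 8 or fewer of 13; 15 recruits per group; 15% dropout. My assumptions: dropout is independent between subjects, the first stage is completed with 7 evaluable subjects, and the 15% applies to the primary outcome, as section 9.3 itself applies it.

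**1. The plan's own figures.** With final number n and at least c favourable outcomes required,

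P(proceed) = sum over x = 5, 6, 7 of C(7,x) p^x (1−p)^(7−x) × P[Bin(n−7, p) ≥ c−x].

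For n = 13, c = 9:
- p = 0.5: 0.1641×0.3438 + 0.0547×0.6562 + 0.0078×0.8906 = 0.099.
- p = 0.8: 0.2753×0.9011 + 0.3670×0.9830 + 0.2097×0.9984 = 0.818.

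Both agree with the stated 0.1 and 80%. A search over designs also returns 4/7, 8/13 as the Simon optimal design.

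**2. The dropout step.** 15 × 0.85 = 12.75, which rounds to 13. Inflating strictly, 13/0.85 = 15.3, or 16 recruits. The gap is one recruit per group.

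**3. Attained number and operating characteristics.** P(N = n) is Binomial(15, 0.85). The middle columns keep the requirement of 9. The last three use the cut-offs proposed below.

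| n | P(N = n) | Type I, c = 9 | Power, c = 9 | Proposed c | Type I | Power |
|---|---|---|---|---|---|---|
| 15 | 0.087 | 0.159 | 0.849 | first 13: 9 | 0.099 | 0.818 |
| 14 | 0.231 | 0.132 | 0.841 | first 13: 9 | 0.099 | 0.818 |
| 13 | 0.286 | 0.099 | 0.818 | 9 | 0.099 | 0.818 |
| 12 | 0.218 | 0.065 | 0.757 | 9 | 0.065 | 0.757 |
| 11 | 0.116 | 0.033 | 0.617 | 8 | 0.096 | 0.792 |
| 10 | 0.045 | 0.011 | 0.376 | 8 | 0.055 | 0.678 |
| 9 | 0.013 | 0.002 | 0.134 | 7 | 0.090 | 0.738 |
| 8 | 0.003 | 0 | 0 | 7 | 0.035 | 0.503 |

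Numbers of 7 or fewer have probability below 0.001 and are counted as not proceeding.

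- P(N < 13) = 0.396 and P(N ≥ 13) = 0.604. All three groups reach 13 with probability 0.604³ = 0.22.
- Average power, at most 13 tested, 9 always required: 0.604×0.818 + 0.218×0.757 + 0.116×0.617 + 0.045×0.376 + 0.013×0.134 = 0.750. Average type I error is 0.078.
- Average power, all evaluable subjects tested, 9 always required: 0.758. Average type I error is 0.091.

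**4. Proposed cut-offs.** Average power: 0.604×0.818 + 0.218×0.757 + 0.116×0.792 + 0.045×0.678 + 0.013×0.738 + 0.003×0.503 = 0.793. The same weights on the type I column give 0.089.

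Resetting the cut-off upwards for 14 or 15 is not an improvement. At least 10/14 gives power 0.798 and at least 11/15 gives 0.773, both below the 0.818 obtained by testing the first 13.

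**5. Recruiting more instead.** With 16 per group (48 in total) and the 8/13 rule capped at 13, P(N ≥ 13) is 0.79 and average power is 0.787. With 17 per group it is 0.805.

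**The case against.** The strongest reply is that nothing has been miscalculated. The design is exactly right at 13, 12.75 is 13 in whole subjects, and power is conventionally quoted at the target number. All of that stands, and the recruitment figure alone would be a rounding matter.

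Three stronger readings are tempting, and the documents do not support them.

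- A reader might infer that the 0.10 error rate is broken. It is at or below 0.10 for every number up to 13, and averages 0.078 to 0.091. It is exceeded only if 14 or 15 outcomes, observed or completed by imputation, are set against the cut-off of 8. The plan does not say this will be done, and its description of stage two reads more naturally as a test of 13.
- A reader might infer that the design is met only when exactly 13 are evaluable, which has probability 0.286. If the two extra recruits are a reserve, it is met in about 60% of groups.
- A reader might infer that no workable cut-off exists at other numbers. Cut-offs within the 0.10 error exist throughout; they are simply not stated.

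Two further objections deserve weight. Section 9.5 does give an approach to missing outcomes, but multiple imputation does not by itself say how imputed results enter a count of favourable subjects. Also, section 9.1 places the 6-month responses among the other outcomes, while section 9.2.1.1 covers both acute and long-term change. If the decisive response is the acute one, dropout over months matters less. But section 9.3 applies the 15% to the primary sample size, so its power statement should be judged on that basis.

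**Conclusion.** The concern holds for power and for the missing decision rule. Under the plan's own dropout rate, a group has about a 40% chance of falling short of 13, and average power is about 75% (0.750 to 0.758, depending on whether subjects 14 and 15 count). That is about five points below the stated 80%. The type I error is not compromised on average. It becomes a problem only in the 14 or 15 case (0.13 and 0.16), which the text leaves open.

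The exact averages rest on the three assumptions listed with the inputs. Dropout that clusters, or that falls in the first stage without replacement, would change them. The absence of a stated cut-off for other numbers does not depend on any of them.

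**What to change.** In section 9.3, keep 15 recruits per group and the 4/7 first stage, and add:

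- The final test uses the first 13 evaluable subjects in enrolment order; proceed if 9 or more are favourable.
- If fewer than 13 are evaluable, proceed only with at least 9/12, 8/11, 8/10, 7/9 or 7/8 (type I error 0.065, 0.096, 0.055, 0.090, 0.035).
- The count uses observed outcomes. The multiple imputation in section 9.5 is a sensitivity analysis.
- Power is 82% at 13 evaluable subjects. At the planned 15% dropout it averages about 79% with these cut-offs (about 75% with the 8/13 rule alone), assuming independent dropout and a complete seven-subject first stage.

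The cost is protocol wording, a slightly less favourable power statement, and the use of subjects 14 and 15 for estimation only. No patients are added. Recruiting 16 per group under the existing rule would add three patients in total and give slightly less power (0.787).
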